5.2.2.1 Adverse Events

Collected Variables:

- Event, i.e. diagnosis or signs/symptoms (text) [CRF – Cumulative adverse event form]
- The start and stop date of the event [CRF – Cumulative adverse event form]
- Outcome of event (categories: recovered/resolved, recovered/resolved with residual effects, recovering/resolving, not recovered/ not resolved, fatal, unknown) [CRF – Cumulative adverse event form]
- Severity (categories: mild, moderate, severe, life threatening or disabling) [CRF – Cumulative adverse event form]
- Treatment (categories: none, specific drug treatment, specific non drug treatment) [CRF – Cumulative adverse event form]
- Relationship with study device (categories: definitive, probable, possible, unlikely, none) [CRF – Cumulative adverse event form]
- Action taken with study device (categories: none, dose reduction temporarily, dose reduced, discontinued temporarily, discontinued) [CRF – Cumulative adverse event form]
- Pattern (categories: every study drug administration, intermittent, continuous, other) [CRF – Cumulative adverse event form]
- Seriousness (yes, no) [CRF – Cumulative adverse event form]

Derived Variables:

- Adverse Events (AEs): an adverse event is any untoward medical occurrence in a subject or clinical study subject administered a pharmaceutical product and which does not necessarily have a causal relationship with this treatment. An AE can therefore be any unfavourable and unintended sign, symptom, or disease temporarily associated with the use of a medicinal product, whether or not considered related to the medicinal product. The definition covers the entire study period, independent of whether IP was administered or not.
- Serious adverse event (SAEs): Any untoward medical occurrence or response to a medicinal product that at any dose: results in death, is life threatening, results in in-subject hospitalization or prolongation of existing hospitalization, results in a persistent or significant disability/incapacity, is a congenital anomaly/birth defect or, important AEs that are not immediately life-threatening or do not result in death or hospitalization but may jeopardize the subject or may require intervention to prevent one of the other outcomes listed.

	Form	Form No.	1M-DMST-011-01-A1
	Statistical Analysis Plan	Page	Page 25 of 69
		Effective Date	07/05/2018

In the analysis serious adverse events will be identified by the variables "Seriousness" (yes, no).

- Related AEs: in the analysis related AEs will be defined as AEs for which the relationship with study device is assessed as "definitive" or "probable" or "possible"
- Severe AEs: in the analysis severe AEs will be defined as AEs for which the severity is assessed as "severe" or "life threatening"
- Subjects who prematurely terminated the Study Due to AE: in the analysis subjects who prematurely terminated the study due to AE are defined as those subjects with an adverse event for which the reason for early termination in the CRF end of study has been recorded as "adverse event"
- Death: death is defined as a fatal outcome of an AE.

Adverse events (AEs) will be reported on a per-subject basis. This implies that even if a subject reported the same event repeatedly, the event will be counted only once. In the latter case, the event will be assigned the worst severity and strongest relationship to the investigational study medication. The presentation of AEs is therefore restricted to the incidence per subject of AEs assigned to the Treatment Period.

Analysis Sets to be used for:	Tables	Safety analysis set
	Listings	Safety analysis set
	Figures	Not applicable

Adverse events will be summarized by default summary statistics by treatment group. Percentages will be calculated relative to the total number of subjects considered valid for the Safety analysis set.

Table 18. Summary of Adverse Events in the Single Dose Phase (Safety set)

Overview of AEs in the single dose phase including the:

- number of subjects with at least one AE.
- number of subjects with at least one device-related AE.
- number of subjects with at least one serious AE.
- number of subjects with at least one severe AE.
- number of subjects who prematurely terminated the study.
- Number of AEs
- Number of serious AEs
- Number of related AEs
- Number of severe AEs
- Number of deaths

Table 19. Summary of Adverse Events in the Multidose Phase (Safety set)

Overview of AEs in the multidose phase including the:

- number of subjects with at least one AE.
- number of subjects with at least one device-related AE.
- number of subjects with at least one serious AE.
- number of subjects with at least one severe AE.
- number of subjects who prematurely terminated the study.
- Number of AEs
- Number of serious AEs
- Number of related AEs
- Number of severe AEs
- Number of deaths

	Form	Form No.	1M-DMST-011-01-A1
	Statistical Analysis Plan	Page	Page 26 of 69
		Effective Date	07/05/2018

Table 20. AEs of Special Interest in the Single Dose Phase (Safety set)

AEs of special interest are symptoms and signs like mild insomnia, elevated levels of liver enzymes, rash, nausea, upper abdominal pain, dizziness, sensitivity to light, irritability, headache, heartburn, and fatigue. A default frequency table will be presented for the AEs of special interest experienced in the single dose phase.

Table 21. AEs of Special Interest in the Multidose Phase (Safety set)

AEs of special interest are symptoms and signs like mild insomnia, elevated levels of liver enzymes, rash, nausea, upper abdominal pain, dizziness, sensitivity to light, irritability, headache, heartburn, and fatigue. A default frequency table will be presented for the AEs of special interest experienced in the multidose phase.

Table 22. AEs by Relationship (Safety set)

A default frequency table will be presented by treatment group for AEs by relationship separately in the two phases of the study.

Table 23. AEs by Severity (Safety set)

A default frequency table will be presented by treatment group for AEs by severity separately in the two phases of the study.

In addition, AE data will be listed as follows:

Listing 18. Listing of AEs: General

All AEs by-subject and within-subject by start date. If the AE is “Ongoing” it will be indicated as such in the field “end date” in the listing. The listing also includes the general demographic data for each subject who experienced an adverse event (gender, age, ethnicity).

Listing 19. Listing of Deaths

List of all deaths in the study; the table also includes the general demographic data for each subject who died (gender, age, ethnicity and race).

Listing 20. Listing of SAEs

Lists all subjects with at least one serious adverse event. The listing also includes the general demographic data for each subject who experienced an adverse event (gender, age, ethnicity).

Listing 21. Listing of AEs Leading to Study Termination

This listing will be presented for those subjects with at least one adverse event leading to study termination: The listing also includes the general demographic data for each subject who experienced an adverse event (gender, age, ethnicity).

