12.9 Analysis of Safety Variables

12.9.1 Adverse Events

	Study Title	Bioavailability Study of COQUN ORAL FORMULATION (CoQ10) administered in Healthy Adults (CoQ10-01)		
	Study ID	VF-BAQ10/2018	Sponsor:	VISUFARMA SpA
	Date	March 03, 2018	Vers.	Final

Safety will be monitored through vital signs, physical exams, clinical laboratory tests (hematology) and adverse events including assessment of relationship to the IP.

Analysis of safety will be performed on the safety set.

The recorded adverse events will be coded according to MedDRA. The adverse events will be summarized by treatment, System Organ Class, preferred-term and intensity.

Nature, incidence and intensity, as well as the investigator's and the sponsor's causality assessment will be reported for each treatment-emergent adverse event. Descriptive summary statistics, e.g., with regard to the incidence of symptoms and the causality assessment, will be presented for the period between V1-V5. Furthermore, all non treatment-emergent adverse events during pre-treatment will be reported between the ICF signature and the first IP intake at V1.

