6. CHANGES TO THE ANALYSIS AS LAID DOWN IN THE PROTOCOL AND AMENDMENTS

No changes to the analysis as laid down in the protocol were made.

1MED Regulatory & Clinical Development	Form	Form No.	1M-DMST-011-01-A1
	Statistical Analysis Plan	Page	Page 31 of 69
		Effective Date	07/05/2018

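### The SAP has no treatment-emergent rule and no pre-treatment AE output, although protocol 12.9.1 calls for both, and its listed fields cannot split AEs that start on the Day -7 dosing date

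*SAP*

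**What the plan says.** **Protocol.** Section 12.9.1 treats two classes of AE differently. Nature, incidence, intensity and "causality assessment will be reported for each treatment-emergent adverse event". Separately, "all non treatment-emergent adverse events during pre-treatment will be reported between the ICF signature and the first IP intake at V1". Section 11.1.6.1 starts AE reporting at written consent, so pre-dose events are meant to be captured. Section 10.5.1 and the flow chart place consent, screening and the single dose under one visit, V1, Day -7.

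**SAP.** Section 5.2.2.1 defines an AE broadly: "The definition covers the entire study period, independent of whether IP was administered or not". It then derives serious, related and severe AEs, discontinuation due to an AE, and death, but not treatment-emergent AEs. Presentation is "restricted to the incidence per subject of AEs assigned to the Treatment Period", and neither section 4.4 nor any other section says what that period is. Tables 18–23 divide AEs into a single-dose and a multidose phase. No table or listing is reserved for AEs before the first intake.

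The timing variable collected is "The start and stop date of the event". Listing 18 is ordered as "All AEs by-subject and within-subject by start date", and its template shows dates without times. Section 4.4 takes Day 1 of the V2–V5 diary as the first intake of study medication. Section 6 states: "No changes to the analysis as laid down in the protocol were made".

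**The concern.** The protocol names a safety report that the SAP does not produce, and the SAP declares no departure. A programmer working from the SAP has no rule for deciding which AEs enter Tables 18–23. The one first-intake date on offer, in section 4.4, falls after the single dose.

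This touches a stated objective, the safety and tolerability of the single 100 mg dose. Headache, dizziness, nausea and fatigue are AEs of special interest. They are also plausible effects of the fast of at least 10 h (protocol 10.6.10) and the 24 h caffeine stop (10.6.16) that precede dosing. If such an event begins after consent but before the capsule and is counted in the single-dose phase, it is attributed to a product not yet taken. If it is left out, no planned output reports it as the protocol asks.

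**Working it through.** The plan gives no figure to reproduce: there is no power calculation and no assumed AE rate. The check sets the rules side by side, asks what dates alone can separate, and then sizes one event.

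**1. Which class each rule gives an AE**

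The protocol does not define treatment-emergent in words. Section 12.9.1 ends the pre-treatment window at the V1 intake and summarises AEs over V1–V5, which implies an anchor at the V1 dose.

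| AE onset | Protocol 12.9.1 (anchor: V1 intake) | Date rule built on SAP 4.4 (anchor: diary Day 1) | SAP Tables 18–23 |
|---|---|---|---|
| After consent, before V1 intake | Pre-treatment, reported separately | Pre-treatment | Not stated |
| Day -7, after V1 intake | Treatment-emergent | Pre-treatment | Single-dose phase |
| Wash-out week | Treatment-emergent | Pre-treatment | Not stated |
| After first multidose capsule | Treatment-emergent | Treatment-emergent | Multidose phase |

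Rows 2 and 3 show the conflict: a rule built on section 4.4 would class every single-dose and wash-out AE as pre-treatment. Rows 1 and 3 show where the phase split gives no answer. Wash-out AEs will be collected, because protocol 10.5.1 issues a diary for the period between V1 and V2.

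**2. What dates alone can separate**

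The SAP lists a date for AE onset. For the V1 intake, section 5.1.4 lists only a yes/no answer. The hh:mm format in section 4.1 is a general display convention and names no AE time.

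- *Consent and dose on the same calendar date* (the flow chart reading): none of the pre-dose window is separable by date.
- *Admission the evening before* (protocol 10.6.13 offers dinner that evening): assume consent by 20:00, a fast of 10 h from then, and dosing at 06:00 or later. Dates separate 20:00 to 24:00, which is 4 h. At least 10 − 4 = 6 h before dosing still fall on the dosing date.

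Under either reading, an AE with onset on the dosing date but before the dose cannot be distinguished from a post-dose AE with the listed variables.

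**3. Size of one event**

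All 24 subjects take the single dose. If a subject's only single-dose-phase AE is in fact a pre-dose event, the proportion of subjects with at least one AE changes by 1/24 = 0.0417, or 4.2 percentage points. This assumes all 24 are in the safety set. A subject who also has a post-dose AE in that phase does not change the proportion, although the count of AEs still rises by one.

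**The case against.** The strongest reply is that this is a short drafting gap in an exploratory study of 24 closely observed healthy subjects.

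- **Source data can probably settle same-day cases.** The Day -7 dose is taken at site under supervision (protocol 10.6.10), AEs go into source documents before the CRF (11.1.1), and queries run until resolved (14.4). The CRF itself is not supplied, so the absence of a time field is inferred from the SAP's variable list and listing templates. This stands, and it limits the claim to what the listed fields allow.
- **The harm is hypothetical.** No pre-dose AE rate is given. Symptoms of fasting or caffeine withdrawal that began before consent fall outside the AE reporting period. This also stands: few events are expected and the window is short.
- **Consent may be given the evening before.** The documents are ambiguous here. If so, some pre-dose events separate by date, but those on the dosing date do not.
- **Listing 18 still shows every AE.** This is true for safety-set subjects, so their pre-dose events are not lost from view. They are unlabelled, however. The safety set also requires randomisation, which happens at V2, so an AE in someone who leaves before V2 would not appear.

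None of this supplies the missing definition, defines the Treatment Period, or reconciles section 4.4 with the protocol's V1 anchor.

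**Conclusion.** The point holds as an undeclared gap between the protocol and the SAP on a secondary safety objective. The conflict is in the text and needs no assumption about AE rates. Its numerical effect is 4.2 percentage points on the single-dose AE rate for each subject whose only event is misplaced. How many such events there will be cannot be estimated from the documents. It is worth correcting because the correction is cheap, but it does not threaten the pharmacokinetic objective.

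Three stronger readings are tempting, and the documents do not support them:

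- *That same-day events can never be classified.* Supervised dosing, source records and queries may resolve them. Only the SAP's listed fields fall short.
- *That one event shifts an arm's single-dose rate by 1/12 = 8.3 points.* Table 18 does have arm columns, but in that phase everyone takes the same dose before randomisation, so a difference between those columns is not a treatment contrast.
- *That the protocol also requires a split on Day 0, before the first multidose capsule.* Section 12.9.1 sets one boundary, the first intake at V1. By V2 subjects have already been dosed.

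**What to change.** 1. On the AE form, record for Day -7 events either the onset time or a flag for before or after first intake. If data are already collected, query same-day Day -7 cases against source before database lock.
2. In SAP 5.2.2.1, define treatment-emergent as onset at or after the V1 intake. State a default for same-day events whose timing cannot be established, and define Treatment Period or remove the term.
3. Reconcile SAP 4.4 with that anchor for AE purposes.
4. State which phase wash-out AEs belong to.
5. Restrict Tables 18–23 to treatment-emergent AEs.
6. Add one listing of AEs from consent to first intake, covering every consented subject, as protocol 12.9.1 asks.

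The cost is one CRF field (or a handful of queries), a few SAP lines and one listing. The SAP's introduction requires it to be final before hard lock, so the SAP changes can be made without touching the protocol.

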8.2.1.3 Safety Analysis

Table 18. Summary of Adverse Events in the Single Dose Phase (Safety set)

Characteristic	Statistic	Treatment A (N=XXX)	Treatment B (N=XXX)	Total (N=XXX)
Number of Subjects With at Least One AE	n (%)	XXX (X.X%)	XXX (X.X%)	XXX (X.X%)
Number of Subjects With at Least One related AE	n (%)	XXX (X.X%)	XXX (X.X%)	XXX (X.X%)
Number of Subjects With at Least One serious AE	n (%)	XXX (X.X%)	XXX (X.X%)	XXX (X.X%)
Number of Subjects With at Least One severe AE	n (%)	XXX (X.X%)	XXX (X.X%)	XXX (X.X%)
Number of Subjects who Prematurely Terminated the Study Due to AE	n (%)	XXX (X.X%)	XXX (X.X%)	XXX (X.X%)
Number of AEs	n (%)	XXX (X.X%)	XXX (X.X%)	XXX (X.X%)
Number of serious AEs	n (%)	XXX (X.X%)	XXX (X.X%)	XXX (X.X%)
Number of related AEs	n (%)	XXX (X.X%)	XXX (X.X%)	XXX (X.X%)
Number of severe AEs	n (%)	XXX (X.X%)	XXX (X.X%)	XXX (X.X%)
Number of deaths	n (%)	XXX (X.X%)	XXX (X.X%)	XXX (X.X%)

N: Number of subjects in specified treatment group

n: Number of subjects with data available

%: Percentage based on N

Notes: a) serious AE are AE with seriousness recorded as "yes";
 b) related AE are AE with relationship with study device recorded as "definitive", "probable", "possible";
 c) severe AE are AE with severity recorded as "severe", "life threatening or disabling";
 d) Subjects who prematurely terminated the Study Due to AE are defined as those subjects with an adverse event for which the reason for early termination in the CRF end of study has been recorded as "adverse event".

 1MED Regulatory & Clinical Development	Form	Form No.	1M-DMST-011-01-A1
	Statistical Analysis Plan	Page	Page 48 of 69
		Effective Date	07/05/2018

Table 19. Summary of Adverse Events in the Multidose Phase (Safety set)

Characteristic	Statistic	Treatment A (N=XXX)	Treatment B (N=XXX)	Total (N=XXX)
Number of Subjects With at Least One AE	n (%)	XXX (X.X%)	XXX (X.X%)	XXX (X.X%)
Number of Subjects With at Least One related AE	n (%)	XXX (X.X%)	XXX (X.X%)	XXX (X.X%)
Number of Subjects With at Least One serious AE	n (%)	XXX (X.X%)	XXX (X.X%)	XXX (X.X%)
Number of Subjects With at Least One severe AE	n (%)	XXX (X.X%)	XXX (X.X%)	XXX (X.X%)
Number of Subjects who Prematurely Terminated the Study Due to AE	n (%)	XXX (X.X%)	XXX (X.X%)	XXX (X.X%)
Number of AEs	n (%)	XXX (X.X%)	XXX (X.X%)	XXX (X.X%)
Number of serious AEs	n (%)	XXX (X.X%)	XXX (X.X%)	XXX (X.X%)
Number of related AEs	n (%)	XXX (X.X%)	XXX (X.X%)	XXX (X.X%)
Number of severe AEs	n (%)	XXX (X.X%)	XXX (X.X%)	XXX (X.X%)

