Fatigue	n (%)	XX (XX.X%)	XX (XX.X%)	XX (XX.X%)

N: Number of subjects in specified treatment group

n: Number of subjects with data available

%: Percentage based on N

RUN: DDMMYYYY HH:MM <1MED > Page X of Y

Table 22. AEs by Relationship (Safety set)

	Statistic	Number of Subjects With at Least One AE in the single dose phase	Number of Subjects With at Least One AE in the multidose phase
TREATMENT A (N=XXX)			
Definitive	n (%)	XX (XX.X%)	XX (XX.X%)
Probable	n (%)	XX (XX.X%)	XX (XX.X%)
Possible	n (%)	XX (XX.X%)	XX (XX.X%)
Unlikely	n (%)	XX (XX.X%)	XX (XX.X%)
None	n (%)	XX (XX.X%)	XX (XX.X%)
TREATMENT B (N=XXX)			
Definitive	n (%)	XX (XX.X%)	XX (XX.X%)
Probable	n (%)	XX (XX.X%)	XX (XX.X%)
Possible	n (%)	XX (XX.X%)	XX (XX.X%)
Unlikely	n (%)	XX (XX.X%)	XX (XX.X%)
None	n (%)	XX (XX.X%)	XX (XX.X%)
TOTAL (N=XXX)			
Definitive	n (%)	XX (XX.X%)	XX (XX.X%)
Probable	n (%)	XX (XX.X%)	XX (XX.X%)
Possible	n (%)	XX (XX.X%)	XX (XX.X%)
Unlikely	n (%)	XX (XX.X%)	XX (XX.X%)
None	n (%)	XX (XX.X%)	XX (XX.X%)

N: Number of subjects in specified treatment group

n: Number of subjects with data available

%: Percentage based on N

Notes:

a) if a subject experienced more than one AE with the same event/diagnosis/sign/symptom, the AE with the strongest relationship will be counted.

RUN: DDMMYYYY HH:MM

<1MED >

Page X of Y

	Form	Form No.	1M-DMST-011-01-A1
	Statistical Analysis Plan	Page	Page 50 of 69
		Effective Date	07/05/2018

Table 23. AEs by Severity (Safety set)

Stat- istic	Treatment A (N=XXX)			Treatment B (N=XXX)			Total (N=XXX)		
	Mild	Moderate	Severe	Mild	Moderate	Severe	Mild	Moderate	Severe
Number of Subjects With at Least One AE In the single dose phase									
n (%)	X (X.X%)	X (X.X%)	X (X.X%)	X (X.X%)	X (X.X%)	X (X.X%)	X (X.X%)	X (XX.X%)	(X.X%)
Number of Subjects With at Least One AE In the multidose phase									
n (%)	X (X.X%)	X (X.X%)	X (X.X%)	X (X.X%)	X (X.X%)	X (X.X%)	X (X.X%)	X (XX.X%)	(X.X%)

N: Number of subjects in specified treatment group

n: Number of subjects with data available

%: Percentage based on N

Notes: If a subject experienced more than one AE with the same event/diagnosis/sign/symptom, the AE with the maximum severity will be counted.

RUN: DDMMYYYY HH:MM

<1MED >

Page X of Y

	Form	Form No.	1M-DMST-011-01-A1
	Statistical Analysis Plan	Page	Page 51 of 69
		Effective Date	07/05/2018

Table 24. Summary of Vital Signs (Safety set)

Characteristic	Statistic	Treatment A (N=XXX)	Treatment B (N=XXX)	Total (N=XXX)
Parameter (unit)				

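### Tables 18 and 19 print adverse event counts as a percentage of subjects, and the once-only counting rule in SAP 5.2.2.1 conflicts with those rows

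*SAP*

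**What the plan says.** SAP 5.2.2.1 sets a per-subject rule for adverse events: "even if a subject reported the same event repeatedly, the event will be counted only once", and the collapsed event takes the worst severity and the strongest relationship. It then draws a general consequence: "The presentation of AEs is therefore restricted to the incidence per subject of AEs assigned to the Treatment Period". For the denominator it states: "Percentages will be calculated relative to the total number of subjects considered valid for the Safety analysis set".

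For Tables 18 (single-dose phase) and 19 (multidose phase), the same section lists two kinds of row. One kind counts subjects with at least one AE, related AE, serious AE or severe AE. The other kind counts events: all AEs, serious AEs, related AEs and severe AEs. No sentence exempts the event rows from the per-subject rule or from the subject denominator.

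The shells in SAP 8.2.1.3 give both kinds of row the same statistic, n (%). Rows such as "Number of related AEs" carry a percentage cell, and the footnotes read "N: Number of subjects in specified treatment group" and "Percentage based on N". The footnote for n also defines it as a number of subjects. A repeated-event note appears only lower down, under Tables 22 and 23; under Table 22 it reads "if a subject experienced more than one AE with the same event/diagnosis/sign/symptom, the AE with the strongest relationship will be counted".

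**The concern.** Tables 18 and 19 are the AE overview for each phase, and safety and tolerability are the study's only secondary objectives (SAP 2.1). Two things look wrong in the event rows.

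First, the percentage divides events by subjects. A reader will take the figure in brackets as the share of the arm affected, because that is what it means in the rows directly above and what the footnote says.

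Second, the text restricts AE presentation to incidence per subject while asking for rows that are not incidence per subject. Taken literally, a row labelled as a number of AEs holds the number of distinct subject-by-event pairs, which is neither a count of events nor a count of subjects. Two programmers working from this SAP could fill the row differently and both cite the document.

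**Working it through.** The documents give no AE figure to reproduce, so the check applies the stated rules to small illustrative cases.

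**Inputs.** N = 12 subjects per arm (SAP 2.5). The counting rule and the denominator are those of SAP 5.2.2.1. The cell format n (%) and the definitions of N and % come from the shells of Tables 18 and 19. The AE numbers are assumed.

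**Formulas.**
- Event row printed: E, with percentage 100 × E / N.
- Share of subjects affected: 100 × S / N, where S is the number of subjects with at least one AE.
- The two agree only when E = S, that is, when every affected subject has exactly one counted AE.

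**Step 1: the percentage, with no repeated events.** If no subject has the same event twice, the once-only rule and a count of all records give the same E.
- 6 subjects with 3 different AEs each: E = 6 × 3 = 18, printed as 18/12 = 150.0%. Subjects affected: 6/12 = 50.0%.
- 3 subjects with 2 different AEs each: E = 3 × 2 = 6, printed as 6/12 = 50.0%. Subjects affected: 3/12 = 25.0%.

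The first result is visibly impossible. The second is the more troublesome because it looks like a valid proportion. Neither depends on which counting rule is chosen.

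**Step 2: the total, with repeated events.** Suppose k = 3 subjects each have one event term recorded m times in a phase. All records give k × m; the once-only rule gives k; the shortfall is 1 − 1/m.

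| m | All records | Once-only count | Shortfall |
|---|---|---|---|
| 1 | 3 (3/12 = 25.0%) | 3 (25.0%) | 0% |
| 2 | 6 (6/12 = 50.0%) | 3 (25.0%) | 50% |
| 5 | 15 (15/12 = 125.0%) | 3 (25.0%) | 80% |

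The shortfall is zero without repeats and grows with them. Counting all records removes the shortfall, but the percentage is then again not a share of subjects.

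**Step 3: severity and relationship.** The once-only rule also assigns the worst severity. One subject with three mild headaches and one severe headache, recorded separately, contributes one AE, which is severe. A count of records gives four AEs, one of them severe. The first convention suits a subject row; it does not describe events.

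**Step 4: rows that are not affected.** The subject rows are correct as specified. The deaths row is also sound, because a subject dies once and the count equals the number of subjects.

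**The case against.** The strongest reply is that the once-only rule was never meant for the event rows. SAP 5.2.2.1 lists those rows separately from the subject rows, the repeated-event note is printed only under Tables 22 and 23, and notes a to d under Tables 18 and 19 say nothing about repeats. A sensible programmer would count every record. In addition, Listing 18 shows all AEs by subject and start date, so with 24 subjects the totals can be recovered, and the raw count and N stand beside any faulty percentage.

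Much of this stands. A reader might infer that the event totals in these tables will be understated. The documents do not establish that. It requires both that the once-only rule is applied to the event rows and that a subject has the same event entered more than once within a phase. The CRF uses a cumulative AE form with start and stop dates and a pattern field that includes an intermittent category (SAP 5.2.2.1). Headaches on several days may therefore be one record, which counts as one AE under either rule. Nor do the documents say that recurrence is expected: the protocol lists reported side effects without frequencies, and a daily diary shows how events are collected, not how often they return.

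A reader might also infer that the rule will hide a tolerability difference between once-daily and twice-daily dosing. That is possible in the multidose phase under the same conditions, but nothing in the documents shows it. It cannot apply to Table 18, because all subjects take the same single dose and are randomised only at Visit 2.

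The reply does not rescue the percentages. Counting every record leaves events divided by subjects, and it contradicts the sentence that restricts AE presentation to incidence per subject.

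**Conclusion.** The point holds for the percentages and, conditionally, for the totals. In the event rows of Tables 18 and 19, the printed percentage is not a proportion of subjects under either counting rule. It is wrong as a share of subjects whenever E differs from S, as it does when affected subjects have more than one counted AE. In the illustrations it overstates the share affected by 25 percentage points (50.0% against 25.0%) and by 100 points (150.0% against 50.0%). These sizes assume 12 subjects per arm and the AE numbers chosen; the defect itself follows from the shells alone.

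The totals are understated only if the once-only rule is applied to these rows and the same event is recorded more than once for a subject in a phase. The illustrated range is 0% to 80%.

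This is a reporting correction that should be made before the tables are programmed. The subject-incidence rows and the primary pharmacokinetic analysis are unaffected.

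**What to change.** 1. In SAP 5.2.2.1, limit the once-only, worst-severity and strongest-relationship rule to the subject-incidence rows and to Tables 22 and 23, and reword the sentence that restricts all AE presentation to incidence per subject.
2. Define the event rows of Tables 18 and 19 (all, serious, related and severe AEs) as the number of AE records on the CRF in that phase. Print them as plain counts without a percentage.
3. Correct the footnotes of both tables so that N and %, and the definition of n as subjects, apply to the subject rows only. The deaths row can stay as it is.

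An event rate per subject-day is optional and not needed to resolve the point. The cost is a few sentences in the SAP and two table shells. No new data are required.
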